#### 6. ANALYSES AND SUMMARIES

#### 6.1. Primary Endpoint: Whole Liver PDFF

Primary Analysis

- Analysis endpoint: Whole liver PDFF
- Analysis time points: Day 42
- Analysis population: Full Analysis set
- Analysis methodology: Natural log-transformed individual relative change (RC) from Baseline to Day 42 in whole liver PDFF will be analyzed using the ANCOVA. The model will include natural log-transformed Baseline whole liver PDFF. Baseline diabetes status will be included as a covariate only if at least 1/3 of the subjects have T2DM.

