4.3. Randomization Criteria

On Day 1, interactive response technology (IRT) will be used to assign each eligible subject a randomization number, with this number recorded on the electronic Case Report Form (CRF). A computer-generated randomization code using the method of random permuted blocks will be utilized to randomize subjects in 1:2:2:2 ratio

(placebo:PF-05221304:PF-06865571:PF-05221304 plus PF-06865571 combination) prior to the first dose of IP, provided subjects satisfy all of the eligibility criteria outlined in Section 4.1 and Section 4.2.

- An attempt will be made to equally balance the number of subjects assigned to each treatment arm within stratum by utilizing a stratification scheme as follows. Subjects will be stratified at randomization (Day 1) by the MRI-PDFF liver fat measurement determined by the Sponsor-identified central imaging vendor of images obtained during Screen 3:
 - Screening liver fat $\ge 8\%$ and <15%;
 - Screening liver fat $\geq 15\%$;
 - Subjects will then be stratified by the presence or absence of T2DM.

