9.1. Sample Size Determination

Approximately 98 subjects will be randomized in a ratio of 1:2:2:2 to four treatment groups A:B:C:D, where A is the placebo group. Assuming an approximate 14% dropout rate this will ensure a minimum of 84 subjects complete the study. This sample size (12 for the placebo group and 24 for the each of monotherapy groups and the combination group) is estimated to provide >90% power to detect a difference of 30% mean reduction in whole liver fat from MRI-PDFF relative to placebo for the PF-05221304 + PF-06865571 combination using a 1-sided Type I error rate of 0.05. This randomization schema will enable detection of a smaller effect requires a larger sample size and hence the sample size is increased for the active arms. With the sample size of 24 completers for each of the PF-05221304 + PF-06865571 combination relative to each monotherapy is approximately 90% using a 1-sided Type I error rate of 0.25. These calculations assume a pooled standard deviation of the log-relative change of 0.32 (based on an internal study).

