9.2. Analysis of the Primary Endpoint

The analysis population for primary endpoint analyses will include all randomized subjects who received at least 1 dose of IP (Full Analysis set).

The primary endpoint will be the relative change from baseline to Day 42 in whole liver PDFF. Baseline will be the closest measurement prior to first dose on Day 1. An analysis of covariance (ANCOVA) will be performed on log-transformed relative change from baseline with treatment and baseline diabetes as factors, and log-transformed baseline whole liver PDFF value as a covariate. Estimates of the mean relative changes between placebo and each active drug arm (PF-05221304 monotherapy, PF-06865571 monotherapy and PF-05221304 plus PF-06865571 combination) at Day 42, and the corresponding 90% confidence interval (CI) will be obtained from the model. Similarly, PF-05221304 plus PF-06865571 combination will be compared to each monotherapy through estimates of the mean relative change and corresponding 50% and 90% confidence intervals. No adjustment for multiple comparisons will be made. If the model does not fit the data group medians and their differences from the placebo median will be presented. The details will be provided in the SAP.

Descriptive summaries of the observed values and percent change from baseline in whole liver PDFF for each treatment group will also be produced.

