# 3.4. Baseline Variables

Baseline variables are those collected on Day 1, prior to dosing, or before Day 1. The demographic data of age, race, weight, height, and body mass index will be summarized by sex at birth and treatment in accordance with the sponsor reporting standards. In addition, the demographic data will be summarized by treatment only in accordance with the sponsor reporting standards. The number and proportion of subjects enrolled in each study site will also be presented.

Subjects will be stratified at randomization (Day 1) by the MRI-PDFF liver fat measurement determined by the Sponsor-identified central imaging vendor of images obtained during Screen 3:

- Screening liver fat  $\geq 8\%$  and <15%;
- Screening liver fat  $\geq 15\%$ ;
- Subjects will then be stratified by the presence or absence of type 2 diabetes mellitus (T2DM).

For Baseline diabetic status, data will be obtained from the case report forms (CRFs). Screening liver fat was used as a binary variable for stratification purposes but Baseline liver fat will be used as a continuous covariate in the efficacy analysis to maximize the utility of information. Baseline diabetic status will only be included as a covariate in the primary analysis (analysis of covariance [ANCOVA]) if at least 1/3 of the subjects have T2DM.

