## Analysis of Covariance

The ANCOVA model will be used with continuous endpoints for landmark (single time point) analyses. The model will include treatment group as fixed effect, Baseline value of the endpoint being analyzed, Baseline whole liver PDFF as covariates. Diabetes status will be included as a covariate for the primary endpoint only if at least 1/3 of the subjects have T2DM. If the endpoint being analyzed is log-tranformed, the Baseline value of the analysis endpoint and the Baseline whole liver PDFF will also be log-transformed. Estimates of treatment effects will be assessed using LSMs and CIs. Estimates of the mean differences for each comparison and the corresponding CI will be obtained from the model. If there are major deviations from the statistical assumptions underlying this model then alternative transformations (eg, log) or non-parametric analyses may be presented. Justification for any alternative to the planned analysis will be given in the study report.

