## 7. INTERIM ANALYSES

If, after randomization of approximately 50% subjects of planned number of subjects, a monthly safety review reveals that the study meets one or more criteria listed in Protocol Section 3.3, an interim analysis will be performed in an un-blinded manner by a prespecified IRC, independent from study team.

Before any interim analysis is initiated, the details of the objectives, decision criteria, dissemination plan, and method of maintaining the study blind as per Pfizer's SOPs will be documented and approved in an IRC charter. The analysis details will be documented and approved in an interim analysis SAP or final SAP.

An IA will be conducted after approximately 50% of randomized subjects reach their Week 6 visit (ie, Visit 10 in Schedule of Activities) or drop out of the study before that visit.

The analysis sets for the IA are:

- 1. Safety Analysis Set: All randomized and treated subjects
- 2. Efficacy/PD Analysis Set: All randomized and treated subjects who completed their Week 6 visit (ie, Visit 10 in Schedule of ActivityActivityActivities) or discontinued the study.

For whole liver PDFF, triglycerides (and total cholesterol, HDL-C, direct LDL-C, Total cholesterol/HDL-C ratio, and non HDL-C, AST, ALT, ALP, GGT), the descriptive summarization and inferential statistical analysis (ANCOVA or MMRM) as indicated in Section 6 will be performed using the Efficacy/PD Analysis Set. Standard safety data as described in the IRC Charter will be summarized using the Safety Analysis Set. The figures related to these descriptive and inferential analyses will be using the "Efficacy/PD Analysis Set".

For whole liver PDFF and triglycerides, additional analysis related to predictive probability will be conducted. The Bayesian predictive probability that the following decision critera will be met at the end of the study given the interim data will be calculated using Pfizer internal validated software. The IRC Statistician will utilize the IA outputs (from ANCOVA analysis for whole liver PDFF and MMRM analysis for triglycerides) to compute the predictive probabilities, and will then provide the probability values to the unblinded programmer to be included in the IA table outputs.

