# The following inputs will be taken from the ANCOVA (liver fat) or MMRM (trigylcerides) interim analysis

i\_r\_nAint <- # sample size for Group 1 at interim

i\_r\_nPint <- # sample size for Group 2 at interim

i\_r\_meanA <- # model-adjusted mean for Group 1 at interim from MMRM or ANCOVA

i\_r\_meanP <- # model-adjusted mean for Group 2 at interim from MMRM or ANCOVA

i\_r\_sigma <- # ssigma estimated at interim from MMRM or ANCOVA

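### The SAP drops diabetes status from the primary ANCOVA when fewer than 1/3 of subjects have T2DM, although the protocol always includes it and randomisation is stratified by it

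*SAP*

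**What the plan says.** **Protocol.** Section 9.2 specifies the primary model thus: "An analysis of covariance (ANCOVA) will be performed on log-transformed relative change from baseline with treatment and baseline diabetes as factors", with log baseline whole liver PDFF as covariate. Diabetes carries no condition. Section 4.3 makes it the second stratification factor, after screening liver fat: "Subjects will then be stratified by the presence or absence of T2DM". Section 9.4 also lists baseline diabetes status in the repeated-measures model for lipids.

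**SAP.** The condition appears three times:
- Section 3.4: "Baseline diabetic status will only be included as a covariate in the primary analysis", followed by the one-third threshold.
- Section 5.2, Analysis of Covariance: "Diabetes status will be included as a covariate for the primary endpoint only if at least 1/3 of the subjects have T2DM".
- Section 6.1: "Baseline diabetes status will be included as a covariate only if at least 1/3 of the subjects have T2DM".

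None of the three gives a reason, the set that supplies the denominator, or the time at which the fraction is assessed. The SAP's lipid MMRM (Section 5.2 and Table 3) has no diabetes term.

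**Interim.** SAP 7 plans an interim analysis when about half the randomised subjects have reached or dropped out before Week 6, where the "inferential statistical analysis (ANCOVA or MMRM) as indicated in Section 6 will be performed using the Efficacy/PD Analysis Set". The predictive-probability code in SAP 9.2 takes its adjusted means from that model, and also "ssigma estimated at interim from MMRM or ANCOVA". SAP 5.1 allows interim results to be used for stopping for futility.

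**The concern.** Three things follow from the text.

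First, the two documents give different primary models when T2DM prevalence is below 1/3. They agree on this term otherwise.

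Second, the term that can drop out is one that randomisation balances. With a stratified factor, the treatment contrast has the smaller variance whether or not the factor is modelled. Leaving it out moves its variance into the residual, so if T2DM is prognostic the reported standard errors and confidence intervals are too wide. SAP 3.4 keeps liver fat continuous to make fuller use of the information, and in the next sentence makes the other stratifier conditional.

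Third, the rule is evaluated twice, on different sets. Near the threshold, T2DM can be in the model at one analysis and out at the other. The predictive probability for E-C1 (combination versus DGAT2 monotherapy on liver fat) would then describe a final analysis that is not the one run.

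The lipid MMRM has a related gap. It is exploratory, but its triglyceride result feeds interim criterion S-C1.

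**Working it through.** **Inputs from protocol 9.1.** 98 randomised 1:2:2:2; 14% dropout; 84 completers (12/24/24/24); SD 0.32 on log relative change; 30% reduction versus placebo at one-sided 0.05; and power for the combination that "relative to each monotherapy is approximately 90% using a 1-sided Type I error rate of 0.25".

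**The plan's own figures.**
- Combination versus placebo: effect −ln 0.7 = 0.357; SE = 0.32 × √(1/12 + 1/24) = 0.1131; power = Φ(0.357/0.1131 − 1.645) = 93.4% (93.1% by noncentral t). This agrees with the stated figure of over 90%.
- 84/(1 − 0.14) = 97.7, so 98.
- Combination versus monotherapy: SE = 0.32 × √(2/24) = 0.0924. The effect with 90% power at one-sided 0.25 is (0.674 + 1.282) × 0.0924 = 0.181, a relative difference of about 16.5%.

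**Assumptions not in the documents.** T2DM prevalence p, and the share R² of variance that T2DM explains. The effect implied on the log scale is b = √(R² × 0.32² / [p(1 − p)]).

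**1. Precision lost by omitting T2DM.** Residual SD rises by 1/√(1 − R²): 1.0%, 2.6% and 5.4% at R² of 2%, 5% and 10%. A simulation (10,000 trials per scenario, T2DM balanced across arms, SD 0.32 before T2DM adjustment, effect 0.181, p = 25% and 30%) gave the following for combination versus monotherapy:

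| R² | implied b | SE ratio, omitted/included | power at 0.25, omitted vs included | power at 0.05, omitted vs included |
|---|---|---|---|---|
| 0 | 0 | 1.0001; 0.9998 | – | – |
| 2% | about 0.10 | 1.010 | 90.4 vs 90.5% (both p) | 61.4 vs 62.1%; 62.2 vs 62.9% |
| 5% | about 0.16 | 1.027 | 90.6 vs 90.9%; 90.5 vs 90.9% | 62.0 vs 63.8%; 61.0 vs 62.8% |
| 10% | 0.22–0.23 | 1.056–1.057 | 91.0 vs 91.5%; 91.3 vs 92.1% | 61.9 vs 65.1%; 62.7 vs 66.3% |

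Paired entries are p = 25%, then p = 30%. Rejection under the null at nominal 0.05, for R² of 2% to 10%, was 0.041–0.047 with T2DM omitted and 0.047–0.051 with it included. Omission is therefore conservative.

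**2. If 0.32 is instead the SD with T2DM in the model.** Omission gives SD = √(0.32² + p(1 − p)b²). At p = 30% and b = 0.1, 0.2 and 0.3, this is 0.323, 0.333 and 0.348. Power against placebo becomes 93.0%, 91.7% and 89.5%, against 93.4%.

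**3. How often the rule bites.** The term enters at 33 or more of 98 at the final analysis, and at 17 or more of 49 at the interim (98/3 = 32.7; 49/3 = 16.3). Exact binomial, with the 49 nested in the 98:

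| prevalence | dropped at final | interim and final differ | 98 randomised vs 84 completers differ |
|---|---|---|---|
| 20% | 99.9% | 1% | 0.2% |
| 25% | 97% | 8% | 3% |
| 30% | 75% | 20% | 11% |
| 33% | 52% | 25% | 12% |
| 40% | 8% | 15% | 5% |
| 50% | 0% | 1% | 0.1% |

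The last column compares 33 of 98 with 28 of 84.

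**4. Effect on the predictive probability.** I used the SAP 9.2 formula with 14 per arm at interim, 28 at the end and sigma 0.32, held the mean difference fixed, and multiplied sigma by √(1 − R²). The largest shift over all mean differences is 0.8, 1.9 and 4.0 points at R² of 2%, 5% and 10%. Where the predictive probability is 0.32 or lower, the shift is at most 2.3 points at R² of 10%.

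**5. Cost of always including T2DM.** Residual degrees of freedom go from 84 − 4 − 1 = 79 to 78. Power against placebo stays at 93.1%.

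**The case against.** The opposing case has real force. Protocol 9 and SAP 2 both let the SAP modify the protocol's analysis, and only a major change to the primary analysis must also go into a protocol amendment. Protocol 9.2 leaves detail to the SAP. The rule is pre-specified and uses a baseline variable pooled over arms, so it cannot be steered by results. SAP 6.1 names the Full Analysis Set in the same list, which makes that the natural denominator; no completer set is defined. The power loss at the planned level is under one point, and if 0.32 is an unadjusted SD, planned power is not reduced at all. The shift in predictive probability is small. The IRC charter, which is not available here, may settle the interim model. The lipid MMRM is exploratory, and both documents allow covariates to be reduced.

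Most of this stands, and it limits the size of the problem. Whether the change is major is a matter of judgement, and nothing here calls it a breach. It does not remove the conflict. The two documents still specify different models below 1/3, no reason is given for omitting a factor used to stratify, and neither document fixes one covariate choice for interim and final. The freedom to reduce lipid covariates is there to improve model fit; it does not explain leaving diabetes out from the start.

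**Conclusion.** The concern holds and should be fixed, as a matter of efficiency and consistency. The treatment contrasts remain unbiased and type I error is not inflated. Under the assumed R² of 2% to 10% and prevalence of 25% to 30%, omission makes the combination-versus-monotherapy standard error 1.0% to 5.7% too wide. Power falls by 0.1 to 0.8 points at one-sided 0.25 and by 0.7 to 3.6 points at one-sided 0.05. The 10% case needs a T2DM effect larger than the 0.181 treatment difference behind the power figure, so it is an upper scenario. If 0.32 is unadjusted, these are forgone gains and not a shortfall against plan.

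The interim mismatch matters mainly for prevalence between about 25% and 40%, where its probability is 8% to 25%; outside that range it fades. When it occurs, the predictive probability moves by a few points at most, but the prediction and the final report no longer use the same model. No passage gives the expected prevalence or the prognostic value of T2DM, so all of these sizes are conditional.

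**What to change.** - In SAP 3.4, 5.2 and 6.1, delete the one-third condition. Include T2DM status (yes/no) as a fixed factor in the primary ANCOVA at both interim and final, as protocol 9.2 states.
- Add T2DM status to the lipid MMRM in SAP 5.2 and Table 3, to match protocol 9.4.
- If the sponsor prefers to keep a rule, state its reason and denominator, make one decision that binds both the interim and the final analysis, and put the same rule in protocol 9.2.

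The cost is SAP wording and one model term: one residual degree of freedom of about 79 at the final analysis. The sample size is unchanged. If T2DM turns out not to be prognostic, including it changes the standard error by about 0.02% or less.

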#### **Reporting results:**

- Raw data: The sample size, mean, STD, median, min and max at Baseline and Day 42 visit will be presented for each treatment arm.
- %CBL: The sample size, mean, STD, median, min and max will be presented for each treatment arm at Day 42. The LSMs and their CI will be exponentiated to provide estimates of the RC which will be converted to percent change as follows: Percent change = 100\* (RC - 1).

*Estimates of the mean relative changes between placebo and each active drug arm* (*PF-05221304 monotherapy, PF-06865571 monotherapy and PF-05221304 plus PF-06865571 combination) at Day 42, and the corresponding 90% CI will be obtained from the model.* The 2-sided p-values will also be presented.

*PF-05221304 plus PF-06865571 combination will be compared to each monotherapy through estimates of the mean relative change and corresponding 50% and 90% CIs.* The 2-sided p-values will also be presented.

# Figures

- Mean + CI plot of the model-derived LSMs in %CFB for all treatment groups including the placebo group with 90% CI will be provided for Day 42 with treatment group on the X-axis.
- Mean + CI plot of the placebo-adjusted LSMs with 90% CI for the each active drug arm (PF-05221304 monotherapy, PF-06865571 monotherapy and PF-05221304 plus PF-06865571 combination) will be provided for Day 42 with treatment on the X-axis.
- Mean + CI plot of the LSM differences with 50% and 90% CIs for the comparison between the PF-05221304 plus PF-06865571 combination and each monotherapy will be provided for Day 42 with treatment on the X-axis.
- Box and whisker plots for individual percent change from Baseline versus treatment will be presented and overlaid with arithmetic means.

# **Reporting results:**

The LSMs, 90% CI for the LSMs, difference between the LSM for each of the 5 treatment comparisons (same as those indicated for the primary analysis), and the corresponding 90% CI (as well as 50% CI for the 2 comparions: the PF-05221304 plus PF-06865571 combination vs, each monotherapy) and the 2-sided p-values will be presented for whole liver PDFF.

# 6.2. Secondary Endpoint(s)

The analyses of safety endpoints will be described in Section 6.6.

# 6.3. Other Endpoints

The below table lists the exploratory endpoints with the corresponding descriptive statistics to be presented. Full analysis set will be utilized.

## Table 2. Exploratory Endpoints - Descriptive Summary

Exploratory Endpoints	Descriptive Statistics
Raw values and % CBL in ALT, AST, Alkaline Phosphatase and GGT, at all relevant collection time point(s) including follow-up	N, Mean, Median, STD, Min and Max at all planned day(s) of collection
Raw values and % CBL in Triglycerides, Total cholesterol, HDL-C, direct LDL-C, Total cholesterol/HDL-C ratio, and non HDL-C, at all relevant collection time point(s) including follow-up	N, Mean, Median, STD, Min and Max at all planned day(s) of collection
	CCI
Page 17	

CCI

# Protocol C3711001 (PF-05221304 and PF-06865571) Statistical Analysis Plan

CCI	
Raw values and % CBL in Apolipoproteins (A1, B100 and C3). at all relevant collection time point(s)	N, Mean, Median, STD, Min and Max at all planned day(s) of collection
	CCI
Raw values and % CBL in plasma PCSK9, at all relevant collection time point(s) including follow-up	N, Mean, Median, STD, Min and Max at all planned day(s) of collection
	CCI

The LSMs, 90% CI for the LSMs, difference between the LSM for each of the 5 treatment comparisons (same as those indicated for the primary analysis), and the corresponding 90% CI and the 2-sided p-values will be calculated using the MMRM/ANCOVA methods described in Section 5.2 as appropriate. The details of the model terms are provided in the below table.

	Page 18	
CCI		

Exploratory Endpoints	Description of the Model Terms
% CBL in ALT, AST, Alkaline Phosphatase and GGT, at all post- Baseline time points	Model: MMRM Response: natural log-transformed RC Covariates: Treatment, Study Day, Treatment*Study Day, log (Baseline value), log (Baseline whole liver PDFF)
% CBL in Triglycerides, Total cholesterol, HDL-C, direct LDL-C, Total cholesterol/HDL-C ratio, and non HDL-C at all post-Baseline time points	Model: MMRM Response: natural log-transformed RC Covariates: Treatment, Study Day, Treatment*Study Day, log (Baseline value), log (Baseline whole liver PDFF)
CCI	
% CBL in fasting plasma PCSK9 at Day 42	Model: ANCOVA Response: natural log-transformed RC Covariates: Treatment, log (Baseline value), log (Baseline whole liver PDFF)

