9. DATA ANALYSIS/STATISTICAL METHODS

Detailed methodology for summary and statistical analyses of the data collected in this study is outlined here and further detailed in a SAP, which will be maintained by the sponsor. The SAP may modify what is outlined in the protocol where appropriate; however, any major modifications of the primary endpoint definitions or their analyses will also be reflected in a protocol amendment.

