9.4. Analysis of Tertiary/Exploratory Endpoints

Percent changes from baseline in LFTs will be summarized; group medians and pairwise differences from the comparators will be presented. Log-transformed relative changes from baseline in lipid panel parameters will be analyzed separately using mixed model for repeated measures (MMRM) with treatment, study day and interaction of treatment with study day as factors, log-transformed baseline values of the dependent variable, baseline diabetes status and log-transformed baseline whole liver PDFF as covariates.

If the model does not fit the data model reduction techniques might be employed; otherwise, group medians and their differences from the placebo median will be presented. Details will be provided in the SAP.

For all other pharmacodynamic endpoints/biomarkers to be included in the CSR observed values, changes from baseline and/or percent changes from baseline will be summarized descriptively at all collection time points. Details and any additional analyses will be described in the SAP.

CCI	

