## Mixed Model for Repeated Measurements (MMRM)

This model will be used for the analysis of endpoints with more than one post-Baseline collection time point. All observed data collected during the post-Baseline treatment period will be utilized. The MMRM analysis will be performed with treatment, study day and treatment-by-study day interaction as fixed effects, Baseline value of the analysis endpoint, and Baseline whole liver PDFF. If the endpoint being analyzed is log-tranformed, the Baseline value of the analysis endpoint and the Baseline whole liver PDFF will also be log-transformed. Repeated measures model with unstructured correlation matrix will be utilized. If this does not converge then compound symmetry structure will be considered. Additionally, the number of covariates may be reduced to improve model fit. Estimates of

treatment effects will be assessed using least square means (LSMs) and CIs at each time point. LSM difference for each comparison along with the CIs and 2-sided p-values will be provided. If there are major deviations from the statistical assumptions underlying this model then alternative transformations (eg, log) or non-parametric analyses may be presented. Justification for any alternative to the planned analysis will be given in the study report.

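### Protocol 9.4 puts baseline diabetes status in the lipid MMRM; SAP 5.2 and the visible lipid row of Table 3 leave out this randomisation stratum without a reason, which can only make the triglyceride intervals mildly conservative.

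*SAP*

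**What the plan says.** Protocol 9.4 analyses log relative change in each lipid parameter by MMRM with treatment, study day and their interaction, plus "log-transformed baseline values of the dependent variable, baseline diabetes status and log-transformed baseline whole liver PDFF as covariates". The diabetes term carries no condition.

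SAP 5.2 describes the MMRM as having "treatment, study day and treatment-by-study day interaction as fixed effects, Baseline value of the analysis endpoint, and Baseline whole liver PDFF". The lipid row of SAP Table 3 repeats this: "Covariates: Treatment, Study Day, Treatment*Study Day, log (Baseline value), log (Baseline whole liver PDFF"). Neither contains diabetes status.

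Protocol 4.3 stratifies randomisation first by screening liver fat, and then: "Subjects will then be stratified by the presence or absence of T2DM". SAP 3.4 repeats the stratification and takes baseline diabetic status from the CRF.

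The SAP does deal with diabetes elsewhere. Its ANCOVA text in 5.2 says "Diabetes status will be included as a covariate for the primary endpoint only if at least 1/3 of the subjects have T2DM". That rule concerns the primary liver-fat analysis.

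SAP 7 and 9.2 take the model-adjusted means and sigma from the triglyceride MMRM to compute the predictive probability of S-C1, which compares the combination with PF-05221304 alone.

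**The concern.** The two documents give different models for one analysis, and a reader cannot tell whether the difference was chosen or overlooked. The one-third rule does not explain it, because that rule governs the primary ANCOVA; in the lipid model the term is absent at any T2DM prevalence. The visible entries of the SAP version history do not mention the change.

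Stratified randomisation balances T2DM across arms, so T2DM differences add little to the true error of a treatment contrast. A model that ignores the stratum still counts those differences as residual noise. The stated standard error then exceeds the real one whenever T2DM predicts lipid change.

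This matters mainly for triglycerides. Protocol 1.6.3 names as an aim the exploration of whether PF-06865571 offsets the triglyceride rise seen with PF-05221304, and S-C1 is built on that contrast.

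**Working it through.** **1. The models side by side**

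| Term | Protocol 9.4 | SAP 5.2 and Table 3 lipid row |
|---|---|---|
| Treatment, day, interaction | yes | yes |
| Log baseline value | yes | yes |
| Log baseline liver PDFF | yes | yes |
| Baseline diabetes status | yes | no |

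**2. Inputs**

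The plan states no power, SD or precision for any lipid, so there is no lipid figure to reproduce. The completer count does reproduce: 98 × 0.86 = 84.28, and 12 + 3 × 24 = 84 (Protocol 9.1).

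Assumed, because the documents are silent:
- residual SD of log change σ = 0.35;
- T2DM share p = 20 to 40%;
- gap in log change between T2DM and non-T2DM subjects δ = 0 to 0.3, the same in every arm;
- permuted blocks of 7 within T2DM strata;
- a single time point standing in for the Day 42 contrast.

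**3. Inflation of the standard error**

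With T2DM balanced across arms, leaving it out moves the between-stratum variance into the residual:

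SE ratio (without / with) ≈ √(1 + p(1−p)δ²/σ²), with σ² = 0.1225.

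| Gap δ | p = 20% | p = 40% | Simulated range |
|---|---|---|---|
| 0 | 1 | 1 | 1.000 |
| 0.1 | √(1 + 0.16 × 0.01/0.1225) = 1.007 | √(1 + 0.24 × 0.01/0.1225) = 1.010 | 1.006–1.010 |
| 0.2 | √(1 + 0.16 × 0.04/0.1225) = 1.026 | √(1 + 0.24 × 0.04/0.1225) = 1.038 | 1.026–1.039 |
| 0.3 | √(1 + 0.16 × 0.09/0.1225) = 1.057 | √(1 + 0.24 × 0.09/0.1225) = 1.085 | 1.058–1.087 |

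The simulation used 4,000 trials per case, 84 subjects, and the combination minus PF-05221304 contrast. It agrees with the formula.

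**4. True sampling error and coverage**

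A second simulation kept two baseline covariates in both models and set one third of each arm diabetic. Shifts are in residual SDs.
- Shift 0.5: the empirical SE of the contrast was 0.292 with and without the term. Mean error was −0.003 in both. Coverage of the 90% interval was 90.7% without the term and 89.9% with it.
- Shift 1.0: coverage was 93.6% without the term and 90.4% with it.

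In the setting of step 3, coverage without the term reached about 92 to 93% at δ = 0.3 and p = 40%. The estimate is unharmed; only its stated uncertainty is too large.

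**5. Cost of including the term when T2DM does not matter**

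At δ = 0, simulation shows the interval widening by about 0.05% with 84 subjects and 0.2 to 0.3% with 42. The formula √((1−R²)(N−6)/(N−7)) seems to show a 0.7% loss at R² = 0 and N = 84. Its R² is the sample value, however, which averages about 1/78 = 1.3% when there is no association. At that value the ratio is √((77/78)(78/77)) = 1.

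**6. Effect on S-C1**

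The partial R² of T2DM is p(1−p)δ²/(σ² + p(1−p)δ²). This gives 0.05 to 0.07 at δ = 0.2 and 0.11 to 0.15 at δ = 0.3.

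In the SAP 9.2 code, take 14 per arm at interim, 28 at the end, confidence 0.95 and target 0. Both the posterior SD and the denominator then equal 0.267s, where s is sigma. The predictive probability is Φ(−1.645 + D/(0.267s)) for an interim difference D in favour of the combination. Set s = 1 without the term and s = √(1−R²) with it, and let D be half the SD from the model without the term:
- without the term: Φ(0.226) = 0.589;
- with it, R² = 0.05: 0.608;
- with it, R² = 0.10: 0.628.

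At D = 0.7 the corresponding values are 0.835, 0.851 and 0.868.

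**The case against.** The strongest reply is that the sponsor was entitled to do this. Protocol 9 says "The SAP may modify what is outlined in the protocol where appropriate", and an amendment is required only for major changes to the primary endpoint or its analysis. Lipid change is tertiary. Protocol 9.4 allows model reduction where fit is poor, and SAP 5.2 allows fewer covariates. The SAP's explicit rule for the primary ANCOVA suggests that dropping diabetes elsewhere was a choice. All of this stands: a reader might infer a protocol breach, and the documents do not support one. What remains is an unexplained difference.

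The second reply is that the gap may be small. Eligibility narrows the contrast: HbA1c above 7.0% is excluded, T2DM subjects may take at most one oral agent, non-diabetic subjects must meet at least two metabolic-syndrome criteria, and fasting triglycerides above 400 mg/dL exclude anyone. Baseline triglycerides and PDFF stay in the model and may absorb part of any T2DM effect. A gap of 0.3 on an SD of 0.35 is 0.86 SD, which is large. This stands too, and is why the effect is given as a range starting at zero.

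Three further inferences fail. A reader might think the treatment estimates become biased or less accurate, or that false-positive risk rises; step 4 shows neither. A reader might see the same conflict in the liver-enzyme rows of Table 3, but Protocol 9.4 plans only summaries and medians there. And a reader might think the interim model needs its own correction, but SAP 7 already uses the Section 6 analysis.

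**Conclusion.** The mismatch is real and should be resolved, at low severity. The protocol fits diabetes status in the lipid MMRM; SAP 5.2 and the visible lipid row of Table 3 do not. Parts of Table 3 are redacted, so nothing can be said about rows that cannot be seen.

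The consequence is conditional. If T2DM is unrelated to lipid change, nothing is lost. If it is prognostic, the standard error is overstated by about 1% at a gap of 0.1, 3 to 4% at 0.2 and 6 to 9% at 0.3, and the predictive probability for S-C1 is a few percentage points too low when the interim difference favours the combination. These sizes rest on the assumed SD, prevalence and gap, on T2DM having the same effect in every arm, and on the single-time-point approximation. The direction, conservative, does not depend on the particular values chosen.

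**What to change.** Add baseline diabetes status (T2DM yes or no) to the MMRM terms in SAP 5.2 and to the lipid row of Table 3, as Protocol 9.4 has it. The interim triglyceride model for S-C1 then changes with it, with no separate edit to SAP 7. If the sponsor prefers to leave the term out, the SAP should say so and give the reason.

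Adding the term to the liver-enzyme rows is optional and would serve consistency only.

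The cost is about two lines of SAP text, one term in existing programs and one degree of freedom. The variable is already collected. The precision lost if T2DM proves irrelevant is about 0.05% of interval width at 84 subjects.
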